7.5.2. Analysis Methods for Clinical (COPD) Exacerbation

As specified in the protocol, because the device-use-measures will be collected continuously over time, these measures could be used to derive many potential predictors of risk. Several analyses are proposed to study correlations between CE-COPD and device-use-measures.

7.5.2.1. Within Patient CE-COPD Analyses

For each CE-COPD event occurring at least 2 weeks after baseline, device-use measures (albuterol use, inhalational flow [MIF], inhalational volume, and time to MIF) will be summarized for each of 2 weeks of interest: first- 'CE-COPD-adjacent week', the week immediately preceding the onset of CE-COPD symptom (ie, day 1 through 7 preceding the date of the CE-COPD symptom onset), and second – 'CE-COPD-Prior Adjacent week', the week preceding that week (ie, during day 8 through 14 preceding the date of the CE-COPD symptom onset). Summary measures of daily and or weekly use will be compared between the two weeks, as proposed below:

Albuterol use measures:

- total number of inhalations in that week
- the maximal daily number of inhalations in that week
- the mean number of daily inhalations (ie, total number of inhalations divided by number of days with number>0)
- occurrence of a single day's albuterol use exceeding 4 inhalations
- occurrence of a single day's albuterol use exceeding 8 inhalations
- occurrence of a single day's albuterol use exceeding 12 inhalations
- number of days when albuterol use exceeding 4 inhalations
- number of days when albuterol use exceeding 8 inhalations
- number of days when albuterol use exceeding 12 inhalations

To note, in this analysis, no inhalation in any day will be taken as a 0 count.

Inhalation flow values parameters:

- maximal daily MIF during the week
- minimal daily time to MIF within a week
- maximal total daily inhalational volume within a week

To note, if no inhalation was taken at a specific day, flow value parameters will be missing and will not be imputed.

Analysis will be based on all patients CE-COPDs for which there are 14 days (or more) prior to the CE-COPD onset, where patient has been on study and CE-COPD free.

Descriptive statistics of use measures in the 'CE-COPD-adjacent week' and 'CE-COPD-Prior Adjacent week' will be presented.

Continuous measures will be compared between the 2 weeks using paired t-test (and Wilcoxon Signed Ranks test) whereas binary patterns will be compared using Mc-Nemar test.

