3.3. Justification for Study Design and Selection of Population

The current study is designed to capture the natural history of CE-COPD and to assess the relationship of exacerbation events with data that are readily obtainable using ABS eMDPI in a routine clinical setting. Thus, there is no control group, and intervention is kept to a minimum (ie, only an eModule in surveillance mode and wearable accelerometers are added to routine care).

Prior work has documented a relationship between SABA usage rates and the subsequent occurrence of CE-COPD. The hypothesis that SABA reliever use predicts short- and long-term exacerbation risk in COPD patients has been evaluated (Jenkins et al 2015). A retrospective analysis of data from a study (Sharafkhaneh et al 2012) comparing budesonide/formoterol 320/9 µg with formoterol 9 µg (both twice daily) in patients with moderate-to-very severe COPD was undertaken; reliever salbutamol 90 µg was provided. The first occurrence of reliever use >4 (low), >10 (medium), and >20 (high) inhalations/day was assessed as a predictor of short-term (3-week) exacerbation risk. Mean daily reliever use in the week preceding the 2-month visit was investigated as a predictor of the long-term (10-month) exacerbation risk, using intervals of 2 to 5, 6 to 9, and ≥10 inhalations/day.

Overall, 810 patients were included (61% male; mean age 63.2 years; post-bronchodilator FEV₁ of 37.7% of predicted). The first occurrence of low, medium, or high reliever use was predictive of an exacerbation within the following 3 weeks; exacerbation risk increased significantly with increasing reliever use. Mean reliever use over 1 week was predictive of long-term exacerbation risk. Patients with a mean use of 2 to 5, 6 to 9, and ≥10 inhalations/day exhibited 21%, 67%, and 135% higher exacerbation rates, respectively, in the following 10 months, compared with those with <2 inhalations/day. Budesonide/formoterol was associated with lower short- and long-term exacerbation risk than formoterol in all reliever-use groups. The authors concluded that SABA reliever use is a predictor of short- and long-term exacerbation risk in moderate-to-very-severe COPD patients with a history of exacerbations receiving budesonide/formoterol or formoterol.

Previous work has also documented a relationship between physical activity and the subsequent occurrence of CE-COPD. In an observational cohort study of 169 persons with COPD

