7.1.2.3. Hypothesis: Albuterol Use Will Increase Several Days Prior to a CE-COPD

The hypothesis under consideration is that albuterol use will increase several days prior to a CE-COPD. Several days will be defined as 7 days prior to the date of the CE-COPD symptom peak for this analysis.

For each subject that experiences at least 1 CE-COPD, Y_1, \dots, Y_7 will represent the number of puffs of albuterol during the 7 days preceding the date of the CE-COPD symptom peak and Y_8, \dots, Y_{14} will represent the number of puffs taken each day during days 8 through 14 preceding the date of the CE-COPD symptom peak. Under the hypothesis of no increased albuterol use

preceding an exacerbation (ie, null hypothesis) assume for subject "xxx" that $Y_i \stackrel{iid}{\sim} \text{Poisson}(\lambda_{xxx})$ for all subjects i. Alternatively, if albuterol use does increase prior to an exacerbation, then

$Y_i \stackrel{iid}{\sim} \text{Poisson}(\lambda_{xxx})$ during day 8 through 14 preceding the date of the CE-COPD symptom peak

and $Y_i \stackrel{iid}{\sim} \text{Poisson}(\lambda_{xxx} + \delta)$ for the immediate 7 days preceding the CE-COPD(s). Also, for random subject effect, assume λ_{xxx} follows some distribution to account for subject to subject variability. Let d_{xxx} will equal to the mean number of puffs during the 7 days immediately preceding the date of the CE-COPD symptom peak minus mean number of puffs during days 8 through 14 preceding the date of the CE-COPD symptom peak. To assess if albuterol usage increases 7 days prior to a CE-COPD, $H_0: \mu_D = 0$, $H_1: \mu_D > 0$ will be tested using a t-test at the 0.05 significance level.

7.1.2.4. Number of Days Prior to the Peak of a CE-COPD When Albuterol Use Increased

Among patients who experienced a CE-COPD, summary statistics of the number of days prior to the peak of a CE-COPD when albuterol use increased, will be presented overall and by moderate CE-COPDs and severe CE-COPDs for 3 thresholds defining an increase in albuterol use;

- (i) First occurrence of a single day increase of 20% from baseline use prior to CE-COPD
- (ii) First occurrence of a single day absolute increase of 2 inhalations from baseline use prior to CE-COPD
- (iii) First occurrence of a single day absolute increase of 4 inhalations from baseline use prior to CE-COPD

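### The test of the study's hypothesis compares the last 7 days with days 8-14 before the event, so a rise in albuterol use longer than a week is understated and a null result cannot be read as no increase

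*SAP*

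**What the plan says.** SAP 7.1.2.3 takes up the hypothesis stated in SAP 1.1 and in the protocol, that albuterol use rises several days before an exacerbation. It fixes the interval: "Several days will be defined as 7 days prior to the date of the CE-COPD symptom peak for this analysis". For each patient with an event, it takes the mean daily puffs over the 7 days before the peak and subtracts the "mean number of puffs during days 8 through 14 preceding the date of the CE-COPD symptom peak". Under its alternative hypothesis, daily use is Poisson at the patient's ordinary rate "during day 8 through 14 preceding the date of the CE-COPD symptom peak" and at that rate plus an increment in the last 7 days. The mean difference, with a one-sided alternative, "will be tested using a t-test at the 0.05 significance level".

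SAP 7.5.2.1 compares the same two weeks counted back from symptom onset; its comparator is "the week preceding that week (ie, during day 8 through 14 preceding the date of the CE-COPD symptom onset". It uses paired t, signed-rank and McNemar tests on a list of use and flow measures. It does not state that the earlier week is unelevated. Events need at least 14 on-study, exacerbation-free days before onset.

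SAP 8 plans no sensitivity analysis. Elsewhere the plan treats the length of the rise as something to be learned. SAP 7.1.2.4 summarises how many days before the peak use first exceeded baseline (study days 1-7), with no 7-day cap. SAP 7.1.2.2, 7.2.2.1, 7.3.2.1 and 7.4.2.1 tabulate values back to 21 days. Protocol 9.5.2.1 says that no robust earlier data guide the choice of usage window.

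**The concern.** A before-and-after contrast measures the full rise only if the comparator week is itself free of it. Section 7.1.2.3 builds that condition into its model, and the plan offers no evidence that days 8-14 are clean. If use begins to climb more than a week ahead, the comparator is already raised and the estimated increase is too small. At stake is the reading of a null or small difference on the study's stated hypothesis: it could mean that use did not rise, or that the rise began before the last week.

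The peak-anchored test is the more exposed of the two. Any days between onset and peak push the start of the rise further back into days 8-14.

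**Working it through.** **The plan's own figure.** The documents give no effect size, SD or power for either test; they give expected events. With 360 evaluable patients, 12 weeks and the mean of 1.05 and 1.14 events per year (SAP 2.3):

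360 × 12/52 × 1.095 = 90.97 events; Poisson 2.5% and 97.5% points are 73 and 110; P(at least 70) = 0.990. The stated 91 (73 to 110) is reproduced and is not in dispute.

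**Events available.** Assume events are uniform over 84 days, and ignore loss from earlier events in the same patient.
- At least 14 prior days: 91 × 70/84 = 75.8, about 76.
- At least 21 prior days: 91 × 63/84 = 68.3, about 68.
- Loss among events eligible for the planned contrast: 7/70 = 10%.

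**Attenuation.** Assume the excess on day k before the anchor is max(0, 1 − (k − 1)/D) for a linear rise over D days, in units of its maximum. W1, W2 and W3 are the mean excess over days 1-7, 8-14 and 15-21. Share lost = 1 − (W1 − W2)/W1 for the planned contrast, with W3 in place of W2 for a days 15-21 reference.

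| Assumed rise | W1 | W2 | W3 | Lost, days 8-14 reference | Lost, days 15-21 reference |
|---|---|---|---|---|---|
| Linear, 7 days | 0.571 | 0 | 0 | 0% | 0% |
| Linear, 10 days | 0.700 | 0.086 | 0 | 12% | 0% |
| Linear, 14 days | 0.786 | 0.286 | 0 | 36% | 0% |
| Linear, 21 days | 0.857 | 0.524 | 0.190 | 61% | 22% |
| Level, 14 days | 1 | 1 | 0 | 100% | 0% |
| Level, 21 days | 1 | 1 | 1 | 100% | 100% |

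If the SD of the difference is unchanged, the number of events needed for equal power grows by (W1/(W1 − W2))². This is 1.3, 2.5 and 6.6 times for the linear rises of 10, 14 and 21 days.

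**Peak anchor.** If the peak falls 3 days after onset (assumed) and use stays at its maximum in between, a linear rise of 7, 14 or 21 days before onset keeps 86%, 47% or 31% of the last-week excess in the peak-anchored contrast.

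**Illustrative power.** One-sided one-sample t-test, alpha 0.05, noncentral t, one difference per event, an assumed standardised true excess of 0.25 or 0.40, and equal SD for both contrasts:

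| Assumed rise | Days 8-14 reference, n = 76 | Days 15-21 reference, n = 68 |
|---|---|---|
| 7 days | 0.70 / 0.97 | 0.65 / 0.95 |
| Linear, 14 days | 0.39 / 0.71 | 0.65 / 0.95 |
| Linear, 21 days | 0.21 / 0.38 | 0.48 / 0.81 |

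**Scope.** The shares lost apply to mean use as in 7.1.2.3 and to the weekly total in 7.5.2.1, which is 7 times that mean. The daily mean in 7.5.2.1 divides by days with use only, so they carry over to it only if the number of use days is the same in both weeks. They do not carry over to the maxima, threshold or flow measures.

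**The case against.** The strongest reply is that the test matches the hypothesis as the SAP defines it. Several days is set at 7, and SAP 7.5.2.2 also uses a 7-day risk horizon. On that definition a longer rise is a different question. This stands as a reason to keep the planned contrast. But the definition fixes a test window; it is not evidence that days 8-14 are unelevated.

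A reader might infer that the plan itself places the run-up at 21 days. The documents do not support that. The cited retrospective analysis in Protocol 3.3 found that a first day above a use threshold "was predictive of an exacerbation within the following 3 weeks". That is a forward risk window and says nothing about how long use stays raised. The 21-day rows are descriptive look-backs. The usage windows given as examples in Protocol 9.5.2.1 reach only a week. Together these passages leave the length open, and no more.

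A reader might also infer that a sustained rise would be hidden and reported as no increase. No section sets such a reporting rule. Sections 7.1.2.2 and 7.1.2.4 would partly show a longer rise, the latter against a baseline taken in study days 1-7. Both are descriptive, however, and 7.1.2.4 records a first single-day crossing, which is not a contrast of weekly means.

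Finally, the study is exploratory, with no multiplicity adjustment, and the shapes used above are invented for illustration. Weeks further apart may also be less correlated, which would raise the SD of the added contrast and offset some of its gain. All of this stands and limits the weight of the point.

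**Conclusion.** The concern holds as a minor point about interpretation. Both formal pre-event comparisons use days 8-14 as comparator. Only 7.1.2.3 models those days as unelevated; in 7.5.2.1 that is at most implied. A rise in weekly mean use that starts more than 7 days before the anchor is attenuated, by the amounts in the table if the rise has those shapes. If the rise fits within 7 days of the anchor, nothing is lost.

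For a rise that builds toward the event, the error is towards the null. A positive result therefore stands, and there is no inflation of type I error from this source. What does not stand is reading a null difference between the two weeks as evidence of no increase.

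**What to change.** Keep the planned contrast and its test. Then:

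- In SAP 7.1.2.3, and for the albuterol-use means or totals in 7.5.2.1, add one supportive pre-specified contrast of days 1-7 against days 15-21, for events with at least 21 on-study, CE-COPD-free days before the anchor.
- Show the three weekly means side by side.
- State that a null difference between days 1-7 and days 8-14 does not exclude a longer rise.

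No new data are needed, because the inhaler timestamps each inhalation. The change is SAP wording, to be approved before database lock as SAP 2.4.2 requires.

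Costs: about 10% of the events eligible for the planned contrast drop out of the added one (about 76 to 68 under uniform timing). There is one more unadjusted exploratory test. The longer gap is more open to time trend and may carry a larger SD. A level rise of 21 days or more would still be missed.

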1. STUDY OBJECTIVES AND ENDPOINTS

1.1. Objectives and Endpoints

The objectives of this study are to explore the pattern and amount of albuterol use (as captured in the albuterol sulfate (ABS) multidose dry powder inhaler with an eModule (eMDPI), alone or in combination with other study data, preceding a moderate or severe CE-COPD (as diagnosed by the investigators per the protocol). The hypothesis is that albuterol use will increase several days prior to a moderate or severe CE-COPD and can serve as a marker of COPD deterioration.

The endpoints of the trial are the primary outcome measure (ie, CE-COPD) and the primary outcome predictor (ie, albuterol use) alone or in combination with secondary predictors (ie, other study data). These predictors of CE-COPD will be modeled to determine which patterns best predict the subsequent development of CE-COPD.

For albuterol use, parameters of interest will include (1) the total number of inhalations in the days preceding the peak of a CE-COPD, (2) the number of days prior to the peak of a CE-COPD when albuterol use increased, and (3) the number of albuterol uses in the 24 hours preceding a CE-COPD. Therefore, endpoints are not designated as either primary or secondary.

In addition to albuterol use, inspiratory flow values (maximal inhalational flow (MIF), inhalational volume, inhalation duration, and time to MIF), sleep disruption index (SDI), total daily steps (TDS), and baseline information regarding disease state and demographics will be studied. These data will be analyzed using both a univariate and multivariate approach, to determine which patterns best predict the subsequent development of a CE-COPD. Inspiratory flow values are obtained from the eMDPI, SDI is obtained for a subset of patients who agree to participate at specific investigational centers (n=100) from an accelerometer worn on the wrist, and TDS is obtained for a subset of patients who agree to participate at specific investigational centers (n=100) from an accelerometer worn on the ankle. Baseline disease state and demographic information will be obtained at screening.

Another objective for this study is to evaluate the safety of ABS eMDPI use in patients with exacerbation-prone COPD.

The safety endpoints for this study include the following:

- adverse event data
- physical examinations

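### Both formal tests of a pre-exacerbation rise compare a later with an earlier week in event patients only, without control for study time, so drift in albuterol use is confounded with a pre-event change

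*SAP*

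**What the plan says.** SAP 1.1 states the hypothesis that albuterol use increases several days before a moderate or severe CE-COPD and "can serve as a marker of COPD deterioration".

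Two sections test it:

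- **SAP 7.1.2.3** is per patient: "For each subject that experiences at least 1 CE-COPD". The tested quantity is mean daily puffs in the 7 days before symptom peak "minus mean number of puffs during days 8 through 14 preceding the date of the CE-COPD symptom peak". With the alternative that the mean difference exceeds zero, it "will be tested using a t-test at the 0.05 significance level". The null model is a Poisson mean that stays constant over the 14 days.
- **SAP 7.5.2.1** is per event and anchored to symptom onset: "Analysis will be based on all patients CE-COPDs for which there are 14 days (or more) prior to the CE-COPD onset". "Summary measures of daily and or weekly use will be compared between the two weeks", days 1–7 against days 8–14. "Continuous measures will be compared between the 2 weeks using paired t-test", with Wilcoxon signed ranks and McNemar tests alongside. No alpha or sidedness is given.

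These are the only hypothesis tests in the SAP. SAP section 8 plans no sensitivity analysis.

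**The concern.** The week nearer the event is always the later week on study. If use is trending for a reason unrelated to the event, the difference picks up the trend. Event patients alone cannot separate the two, because every pair has the same time order.

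The plan gives reasons to expect some trend. Patients give up their other short-acting agents, including maintenance use, for a new device at the start of recording (Protocol 4.1, criterion g). The qualifying exacerbation may fall at any time in the previous 12 months, and Protocol 4.2 sets no minimum interval since it, so some patients may still be recovering.

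What is at stake is the study's one stated hypothesis. A rise seen only in event patients is also weak support for a marker until the same rise is shown to be less common over comparable event-free weeks.

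**Working it through.** **1. The plan's event count.** Inputs from SAP 2.3: 360 evaluable patients and rates of 1.05 and 1.14 per year (mid-point 1.095). 360 × 1.095 × 12/52 = 90.97, which matches 91. The Poisson 2.5% and 97.5% quantiles are 73 and 110, and P(≥70) = 0.990. The plan's figures reproduce. It states no power or variance for either test.

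**2. Observations per test.** Two full prior weeks are needed, so events must fall in days 15–84 (constant rate assumed).
- Events (7.5.2.1): 91 × 70/84 ≈ 76.
- Patients (7.1.2.3): 360 × (1 − exp(−1.095 × 10/52)) ≈ 68.
- Patients with no event in 12 weeks: 360 × exp(−1.095 × 12/52) ≈ 280.

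**3. What the difference estimates.** With mean use λ per day, weekly drift g and no event effect, the expected later-minus-earlier difference is gλ, not 0.

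**4. Rejection with no true rise.** Let φ be the variance/mean ratio (φ = 1 is the SAP's Poisson model). SD of the difference = √(2λφ/7). Noncentrality = gλ√n / SD. Rejection is the noncentral-t probability beyond the one-sided 0.05 critical value on n − 1 df. Example with λ = 4, φ = 1, n = 76, g = 0.03: SD = √(8/7) = 1.069; noncentrality = 0.12 × 8.718 / 1.069 = 0.979; rejection 0.25.

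The values of g, λ and φ are assumptions; the documents give none of them.

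| Weekly drift | n = 76, 4/day, φ = 1 / 2 / 3 | n = 68, 4/day, φ = 1 / 2 / 3 | Range over 2–6/day, both n |
|---|---|---|---|
| +1% | 0.09 / 0.08 / 0.07 | 0.09 / 0.08 / 0.07 | 0.06–0.11 |
| +3% | 0.25 / 0.17 / 0.14 | 0.23 / 0.16 / 0.13 | 0.10–0.32 |
| +5% | 0.49 / 0.31 / 0.24 | 0.45 / 0.29 / 0.22 | 0.15–0.63 |
| −3% | 0.0045 / 0.010 / 0.014 | 0.005 / 0.011 / 0.015 | 0.002–0.022 |

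The one-sided level is stated only for 7.1.2.3. If 7.5.2.1 is two-sided at 0.05, then n = 76, 4/day and +5% gives 0.36 (φ = 1) or 0.15 (φ = 3).

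**5. Simulation** (4,000 runs per setting, about 76 events, 4/day; three event-free control differences per event over the same study days, with controls sharing the cases' drift):
- No true rise, drift +0.2/day per week (5% of 4): 40% rejection as planned (20% at φ = 3), 5% with controls. The formula gives 49% and 24%, so its values run somewhat high.
- True rise 0.5/day, φ = 3, drift −0.2: power 51% as planned, 75% with controls.
- True rise 0.5/day, φ = 3, no drift: 73% as planned, 63% with controls. This is the price of control when there is nothing to control.

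**6. Drift confined to the first 4 weeks.** Only events in days 15–28 are affected, 14/70 = 20% if evenly spread. Average drift is then 0.2g, and at 4/day rejection is 0.06–0.07 for 3% and 0.07–0.09 for 5%.

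**7. Why event-free weeks matter for a marker.** 91 events in 360 × 84 = 30,240 patient-days is a 7-day risk of about 2.1%. At an assumed sensitivity of 0.7 and a 7-day false-alarm probability of 0.05, 0.10 or 0.30, the share of alarms that are false is 77%, 87% or 95%.

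**The case against.** A reader might infer that the plan ignores event-free patients and has no false-alarm information. The documents do not support that:

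- SAP 7.1.2.4 summarises, in patients without a CE-COPD, the proportion of study days above a use threshold, with 95% CIs.
- SAP 7.5.2.2 follows every patient who first exceeds 4, 8 or 12 inhalations in a day. One minus the 7-day Kaplan–Meier risk is the share of first crossings not followed by an event.
- The figure in SAP 7.1.2.2 plots mean use by study day and CE-COPD status, and would display drift in event-free patients.
- The predictive models are assigned to a separate data analytics report (SAP 7.5.3), not cancelled.

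These points stand, but none repairs the two tests. The bracketed definition in 7.1.2.4 counts days above 4 inhalations, while its list names first occurrences of changes from baseline. SAP 7.5.2.2 uses first crossings of absolute levels only. Neither says how often the tested week-on-week rise occurs without an event. The all-days analysis in 7.5.2.3 is offered as one possibility.

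A reader might also infer that the bias is known to be upward. It is not. Recovery from an earlier exacerbation lowers use, which makes the one-sided test conservative. The device switch is a step on Day 1, and a continuing climb after it is speculative. Both effects should be strongest early, which favours the smaller figures in step 6.

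Finally, the study is exploratory and the within-patient comparison sits beside other analyses. That excuses the absence of multiplicity control. It does not remove a time-order bias from the test of the stated hypothesis.

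**Conclusion.** The point holds for the two tests. They cannot tell a pre-event change from drift over study time, and the error can go either way. Under the assumed ranges (drift +1% to +5% per week throughout, 2–6 inhalations/day, variance/mean 1–3, n of 68–76), false rejection runs from about 6% to 63% against a nominal 5%. It is about 6% to 9% at 4/day if drift of 3% to 5% is confined to the first four weeks. A 3% weekly fall lowers rejection to about 0.2% to 2% and can hide a real rise. Neither the existence of drift nor its direction is established by the documents, so these figures show sensitivity and do not predict what will happen. False-alarm information exists, but it is not linked to the contrast being tested. This is a cheap improvement worth making, not a flaw that invalidates the study.

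**What to change.** Keep the paired tests, and add a study-time-controlled version to SAP 7.1.2.3 and 7.5.2.1:

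- For each qualifying CE-COPD, take (say) 5 patients who are on study and CE-COPD-free over the same study days, matched on baseline albuterol use; alternatively use a relative (log-rate) contrast. Matching matters because Protocol 3.3 reports that heavier users exacerbate more. If drift is proportional and controls average 2/day against 4/day in cases, subtracting absolute differences leaves the error at 0.08–0.12 for 3% drift.
- Test the case two-week difference minus the mean matched control difference. Cluster or bootstrap by patient: 76 × 5 = 380 control slots exceed the roughly 280 event-free patients, so controls will be reused.
- Report the share of control week-pairs with an equal or larger rise.
- Base the marker conclusion on the controlled contrast.

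The cost is SAP text and some programming on data already collected. With 5 controls per event the standard error grows by √(1 + 1/5) = 1.095, about 10%, and slightly more with reuse. Some power is lost if there turns out to be no drift.

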7.5. Clinical Exacerbation of COPD

7.5.1. Definition of Clinical Exacerbation of COPD

A CE-COPD is the primary outcome measure of this study. In this study, a CE-COPD is an occurrence of either a “severe CE-COPD” or a “moderate CE-COPD.” “Mild CE-COPD” is defined below for investigator information but is not used either for entry criteria or as a measure in this study.

- Severe CE-COPD is defined as an event that involves worsening respiratory symptoms for at least 2 consecutive days requiring treatment with systemic corticosteroids (SCS; at least 10 mg prednisone equivalent above baseline [Table 2]) and/or systemic antibiotics and a hospitalization for CE-COPD.
- Moderate CE-COPD is defined as an event that involves worsening respiratory symptoms for at least 2 consecutive days requiring treatment with SCS (at least 10 mg prednisone equivalent above baseline [Table 2]), and/or systemic antibiotics, and an unscheduled encounter (such as a phone call, an office visit, an urgent care visit, or an emergency care visit) for a CE-COPD, but not a hospitalization.
- Mild CE-COPD is defined as a worsening of respiratory symptoms for at least 2 consecutive days requiring self-management by the patient, such as increased inhaler use, but not requiring treatment with SCS and/or antibiotics, nor an unscheduled visit of any kind.

Table 2: Systemic Glucocorticoid Treatment Equivalent to 10 mg of Prednisone

Glucocorticoid Treatment	Dose (mg) Equivalent to 10 mg of Prednisone	Comment
Cortisone	50	Includes parenteral
Hydrocortisone	40	Cortisol
Prednisolone	10	-
Methylprednisolone	8	Medrol: includes parenteral SOLU-MEDROL®
Triamcinolone	8	-
Betamethasone	0.4	-
Dexamethasone	0.4	Oral or parenteral DECADRON®

The designation of a CE-COPD as moderate or severe is denoted by the response to the CRF question “Severity” on the Clinical Exacerbation of COPD CRF page regardless of whether the following CRF questions are answered in the negative or missing:

- “The treating physician elects to administer prednisone (or equivalent glucocorticoid treatment) at least 10 mg prednisone equivalent above baseline, for at least 3 days”
- An unscheduled provider visit such as an office visit, telephone call, urgent care visit, emergency care visit, or hospitalization

A patient may experience more than 1 CE-COPD during the study period.

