7.5.2.3. All Days Analysis (Only CE-COPD-free Days)

This analysis will be performed by the data analytics group. Additional details may be specified in a separate report. One possible analysis is presented below:

For each patient, all study days where the patient was CE-COPD free will be the unit of this analysis. There are various ways to summarize albuterol use on this, for example by looking at:

- daily number of inhalations
- albuterol use exceeding 4 inhalations (Yes/No)
- albuterol use exceeding 12 inhalations (Yes/No)

Exploratory analyses using all these patient days can be performed to predict occurrence of CE-COPD event in the next day (for example, using logistic regression). Exploratory predictive analyses will be reported separately.

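### The paired tests in SAP 7.5.2.1 take every qualifying exacerbation as an independent unit although a patient may contribute more than one; the standard errors may be slightly too small

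*SAP*

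**What the plan says.** SAP 7.5.2.1 sets the unit at the start: "For each CE-COPD event occurring at least 2 weeks after baseline". It compares days 1 to 7 before symptom onset with days 8 to 14. Eligibility is also set by event: "Analysis will be based on all patients CE-COPDs for which there are 14 days (or more) prior to the CE-COPD onset", with the added condition "where patient has been on study and CE-COPD free". Nothing limits a patient to one event.

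The tests are standard ones: "Continuous measures will be compared between the 2 weeks using paired t-test", with a Wilcoxon signed-rank test alongside, and "binary patterns will be compared using Mc-Nemar test". The section lists twelve measures, nine of albuterol use and three of inhalation flow. It names no first-event rule, patient-level average, random effect, GEE or robust variance.

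SAP 7.5.1 states that repeat events are expected: "A patient may experience more than 1 CE-COPD during the study period".

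Two neighbouring sections matter for the scope of the point. SAP 7.1.2.3, the formal test of rising albuterol use, defines one difference per subject. SAP 7.5.2.3 describes an analysis in which "all study days where the patient was CE-COPD free will be the unit of this analysis", but offers it as one possibility, with logistic regression as an example, and leaves it to the data analytics group. SAP 8 plans no sensitivity analysis.

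**The concern.** A paired test removes the dependence between the two weeks of one event. It does nothing about dependence between two events of the same patient. Some patients may regularly step up their inhaler use before an exacerbation and others may not. Two differences from one patient then resemble each other and carry less information than two differences from different patients. The tests in 7.5.2.1 count them as full, separate observations, which makes standard errors too small and p-values too low.

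The event-level mean also gives a patient with two events twice the weight of a patient with one. That can be a legitimate target (the average event rather than the average patient), but the section does not say which is meant. With no sensitivity analysis planned, nothing else in the SAP would show the size of either effect.

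**Working it through.** **Reproducing the plan's event count.** Inputs from SAP 2.3: 360 evaluable patients, annual rates of 1.05 and 1.14 (mean 1.095), 12 weeks.

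- Expected events: 360 × 1.095 × 12/52 = 90.97, matching the stated 91.
- Poisson 2.5% and 97.5% points: 73 and 110, matching the stated range.
- Probability of at least 70 events: 0.9901, matching the stated figure of above 0.99.

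**Repeat events before the 14-day rule.** The mean per patient is 90.97/360 = 0.2527. Under a Poisson model:

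- Patients with at least one event: 360 × (1 − e^(−0.2527)) ≈ 80.
- Patients with two or more: about 10.
- Events per affected patient: 0.2527/(1 − e^(−0.2527)) ≈ 1.13.

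**Repeat events after the 14-day rule.** Events were simulated for 360 patients over 84 days, keeping only those with 14 days on study and exacerbation-free before onset. Two inputs are assumptions, not in the documents: an event duration of 12 days, and gamma-distributed differences in risk between patients (frailty variance 0 to 4).

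**Effect on the tests.** With m the number of eligible events per contributing patient and ρ the within-patient correlation of the week-to-week differences (also assumed):

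- Design effect: DE = 1 + (Σm²/Σm − 1) × ρ.
- Correct SE / reported SE = √DE.
- True two-sided level of a nominal 0.05 test = 2 × [1 − Φ(1.96/√DE)].

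The section states no level or sidedness; 0.05 two-sided is assumed.

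| Frailty variance | Eligible events | Patients | Patients with repeats | Σm²/Σm | SE ratio at ρ = 0.3 / 0.5 / 1 | True level at ρ = 0.3 / 0.5 / 1 |
|---|---|---|---|---|---|---|
| 0 | 70.4 | 67.8 | 2.7 | 1.075 | 1.011 / 1.019 / 1.037 | 0.053 / 0.054 / 0.059 |
| 1 | 66.2 | 61.8 | 4.3 | 1.130 | 1.019 / 1.032 / 1.063 | 0.055 / 0.058 / 0.065 |
| 2 | 61.4 | 56.5 | 4.9 | 1.160 | 1.024 / 1.039 / 1.077 | 0.056 / 0.059 / 0.069 |
| 4 | 54.9 | 49.2 | 5.7 | 1.209 | 1.031 / 1.051 / 1.100 | 0.057 / 0.062 / 0.075 |

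Worked example, last row at ρ = 0.5: DE = 1 + 0.209 × 0.5 = 1.105; √1.105 = 1.051; 1.96/1.051 = 1.865; level 0.062. At ρ = 0, DE = 1 and nothing changes.

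**Stress case.** In the table, 4% (2.7/67.8) to 12% (5.7/49.2) of contributing patients have repeats. If the share were 20% of 55 patients (17% with two events, 3% with three), the paired t-test on all events had simulated levels of 0.062, 0.078 and 0.10 at ρ = 0.3, 0.5 and 1. One mean difference per patient kept the level at about 0.05 throughout (4,000 runs per setting).

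**The case against.** The strongest reply is that this hardly matters. The 14-day rule keeps the windows of successive events from overlapping and removes most repeats. Pairing removes a patient's stable level of use, so the correlation that counts is that of the differences, which may be near zero. The section sets no significance level or decision rule and runs 21 unadjusted tests in an exploratory study (nine continuous measures tested two ways, three binary ones by McNemar). A change of a few percent in a standard error would not alter how these are read. Event weighting also fits the question the section asks. All of this stands. It makes the effect small and conditional, but it does not supply the missing rule for repeat events.

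Three stronger readings are tempting, and the documents do not support them.

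- A reader might infer that the standard errors and p-values in 7.5.2.1 are too small in any case. That needs positive within-patient correlation of the differences, which the documents do not quantify.
- A reader might infer that the patient-day regression in 7.5.2.3 treats days as independent. The SAP gives that model only as an example and names no variance method, so it is silent. Nor do many days per patient shrink the standard error by themselves: for first events, a pooled patient-day logistic model is a discrete-time survival likelihood. In simulation under no effect, the ratio of true to model-based standard error was 0.94 with no frailty, and also 0.94 when the predictor varied only within patients. It was 1.04, 1.11 and 1.16 to 1.21 at assumed frailty variance 1, 2 and 4 with a predictor that differs between patients. Simulation error on these ratios is about 3% to 4%.
- A reader might extend the point to the formal hypothesis test in 7.1.2.3. That test uses one difference per subject and is not affected as written, although it does not say which event is used for a patient with several.

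**Conclusion.** The point holds for 7.5.2.1 and is minor. The section tests events as independent units, the SAP allows several per patient, and no method accounts for this. With about 55 to 70 eligible events in 49 to 68 patients, the correct standard error is about 1% to 5% larger than the reported one at correlation 0.3 to 0.5, giving a true level of about 0.053 to 0.062. At correlation 1 it is at most about 10% larger over the frailty range examined (level up to 0.075), and at correlation 0 there is about no effect. A higher share of patients with repeats than the plan's rates imply would enlarge the effect, as the stress case shows.

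The event rate and patient numbers are the plan's. The correlation, frailty variance and 12-day event duration are assumptions. The conclusion does not cover 7.1.2.3, and for 7.5.2.3 it is advice on an optional analysis, not an error in the SAP.

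**What to change.** Add a sentence to SAP 7.5.2.1 stating whether the target is the average event or the average patient, and choose one of the following:

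- Keep all qualifying events and use a patient-clustered method: GEE or a mixed model with patient as the cluster, or a bootstrap that resamples patients.
- Use one mean difference per patient for the t and Wilcoxon tests, and the first qualifying event per patient for McNemar.

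The first option uses all the data but replaces the named tests, because the ordinary Wilcoxon and McNemar tests have no clustering option. The second keeps the named tests, weights patients equally in the t and Wilcoxon tests, and leaves a few repeat events out of McNemar; only about 3 to 6 patients are concerned. Either way, intervals may widen slightly.

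If the patient-day model of 7.5.2.3 is run with repeat events included, patient-clustered standard errors are advisable and can be specified in the data analytics group's separate report. SAP 2.4.2 allows amendments before database lock.
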